8.3.3.3 EXPECTEDNESS

Risk analysis conducted by BrainQ Technologies Ltd. shall be used as a basis for identifying anticipated AEs/ADEs characterized by their nature, incidence, severity, and outcome. In general, an AE/ADE will be considered unexpected if the nature, severity, or frequency of the event is not consistent with the risk information previously described for the investigational device. The potential expected (anticipated) side effects, based on the risk analysis, are listed in § 2.3.1 above.

SAEs known to occur with a frequency >1% in the normal course of patients with acute ischemic stroke under standard medical management will generally be rated as attributable to the subject's underlying condition (please refer to the list provided as an appendix to the MOP).

For reporting to regulatory authorities, the Sponsor or Sponsor's designee (Medical Monitor/Expert) will be responsible for determining whether an SAE/SADE is expected (anticipated) or unexpected (unanticipated) in this study³⁸.

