8.3.3.2 RELATIONSHIP TO STUDY INTERVENTION

For all collected AEs, the Investigator who examines and evaluates the subject will provide the Sponsor with his/her assessment of the AE causality based on temporal relationship and his/her clinical judgment³¹. The degree of certainty about causality will be graded using the categories in [Table 4](#) below³².

³¹ Procedure related events refers to the procedure related to the initial application of the investigational medical device only and therefore not to any other procedures or treatments applied later throughout the clinical investigation, for instance to treat (serious) adverse events (MEDDEV 2.7/3 revision 3 - GUIDELINES ON MEDICAL DEVICES - CLINICAL INVESTIGATIONS: SERIOUS ADVERSE EVENT REPORTING UNDER DIRECTIVES 90/385/EEC AND 93/42/EEC)

³² Based on the EU medical device coordination group (MDCG) guidance 2020-10/1 *Safety reporting in clinical investigations of medical devices under the Regulation (EU) 2017/745*. Although originally proposed for serious adverse events, it is suitable for non-serious events as well.

The Sponsor and the Investigators will distinguish between the serious adverse events related to the investigational device, those related to the procedures (any procedure specific to the clinical investigation), and those unrelated to either the investigational device or study procedures. An adverse event can be related both to procedures and the investigational device.³³

Table 4. Causality of adverse events

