	
Relationship to the device, comparator or procedures can be excluded when:
 
 – the event has no temporal relationship with the use of the investigational device, or the procedures related to application of the investigational device; – the serious adverse event does not follow a known response pattern to the medical device (if the response pattern is previously known) and is biologically implausible; – the discontinuation of medical device application or the reduction of the level of activation/exposure - when clinically feasible - and reintroduction of its use (or increase of the level of activation/exposure), do not impact on the serious adverse event; – the event involves a body-site or an organ that cannot be affected by the device or procedure; – the serious adverse event can be attributed to another cause (eg, an underlying or concurrent illness/ clinical condition, an effect of another device, drug, treatment or other risk factors); – the event does not depend on a false result given by the investigational device used for diagnosis³⁴, when applicable; 
In order to establish the non-relatedness, not all the criteria listed above might be met at the same time, depending on the type of device/procedures and the serious adverse event.

Possible	The relationship with the use of the investigational device or comparator, or the relationship with procedures, is weak but cannot be ruled out completely. Alternative causes are also possible (e.g. an underlying or concurrent illness/ clinical condition or/and an effect of another device, drug or treatment). Cases where relatedness cannot be assessed, or no information has been obtained should also be classified as possible.
Probable	The relationship with the use of the investigational device or comparator, or the relationship with procedures, seems relevant and/or the event cannot be reasonably explained by another cause.
Causal relationship	
The serious adverse event is associated with the investigational device, comparator or with procedures beyond reasonable doubt when:
 
 – the event is a known side effect of the product category the device belongs to or of similar devices and procedures;

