10.1.2 STUDY DISCONTINUATION AND CLOSURE

This study may be temporarily suspended or prematurely terminated if there is sufficient reasonable cause. Written notification, documenting the reason for study suspension or termination, will be provided by the suspending or terminating party to study participants, Investigator(s), Sponsor and regulatory authorities, where applicable. If the study is prematurely terminated or suspended, the Investigator will promptly inform study participants, IRB/EC, and Sponsor, and will provide the reason(s) for the termination or suspension. Study participants will be contacted, as applicable, and be informed of changes to study Visits schedule.

Circumstances that may warrant termination or suspension include, but are not limited to:

- Determination of unexpected, significant, or unacceptable risk to participants;
- Determination of possible serious health threat;
- Demonstration of efficacy that would warrant stopping;
- Insufficient compliance to protocol requirements and/or good clinical practice and/or regulatory requirements;
- Data that are not sufficiently complete and/or evaluable;
- Insufficient study enrollment;
- Investigational product supply or manufacturing issues;
- The Sponsor's decision to modify or discontinue product development;
- A request to discontinue the study by a regulatory or health authority.

	The efficacy of a frequency-tuned electromagnetic field treatment in facilitating the recovery of subacute ischemic stroke patients – a pivotal study		
	No. BQ5	Ver. 4	Page 89 of 150

Study-wide administration of study device will be halted if Grade ≥ 4 AEs determined to have “probable” or “causal” relationship are reported to the Sponsor. The Sponsor will notify the Investigators immediately when the event is reported, and enrollment screens will stop accepting new study participants. Where required, the Sponsor will inform the regulatory authorities of the temporary halt and the disposition of the study.

Similarly, if suspicion of an unacceptable risk, including serious health threat, to subjects arises during the trial, or when so instructed by the IRB/EC or regulatory authorities, the Sponsor shall suspend the clinical investigation while the risk is assessed. The Sponsor shall terminate the clinical investigation if an unacceptable risk which cannot be mitigated is confirmed⁵³.

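### The Expectedness section contains a presumption of cause for common post-stroke SAEs that is not reconciled with case-by-case causality grading and can only lower the related-SAE count

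*Protocol*

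**What the plan says.** **Section 8.3.3.3, Expectedness.** The rule covers "SAEs known to occur with a frequency >1% in the normal course of patients with acute ischemic stroke". Such events "under standard medical management will generally be rated as attributable to the" patient's underlying illness. The events themselves are not named in the protocol: "please refer to the list provided as an appendix to the MOP".

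**Section 8.3.3.2, Relationship to Study Intervention.** For all collected adverse events, "the Investigator who examines and evaluates the subject will provide the Sponsor with his/her assessment of the AE causality", and the grade rests on timing and clinical judgment. The sponsor or its medical monitor also reviews every event and documents its relationship in writing. If the two differ, both opinions are passed on. Under Table 4, 'possible' is available when an underlying illness is an alternative cause. The table adds: "Cases where relatedness cannot be assessed, or no information has been obtained should also be classified as possible".

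**Where relatedness is used.** The safety endpoint in sections 1.1 and 3 is serious procedure- or device-related adverse events. Section 10.1.2 begins its halt rule with "Study-wide administration of study device will be halted if Grade" and applies it to events of Grade 4 or higher determined to be probable or causal.

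**Where relatedness is not used.** Section 9.4.4 names the cumulative incidence of adverse events per group as the primary safety variable. It compares event rates by Fisher's exact test without restriction to related events, and has serious events listed and discussed individually.

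**The concern.** Two different questions are run together. Expectedness asks whether an event is consistent with what is already known, and section 8.3.3.3 itself ties it to the risk information described for the device. Causality asks whether the device or procedure contributed in this patient. An event can be common after stroke and still have been caused by the device. A rule that moves from 'common after stroke' to 'attributable to the stroke' answers the second question with evidence on the first.

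The declared safety endpoint depends on the causality grade. If raters follow the presumption, a listed event that case review would have called related can leave the endpoint. No event can enter it by the same route. Section 2.3.1 names fracture from a fall during lower-extremity exercises, and seizure from device malfunction, as study risks. Both can also occur in the course of stroke. Whether either is on the list cannot be checked, because the list is in the manual of procedures.

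**Working it through.** The protocol derives no figure from the 1% threshold, so there is nothing to reproduce. The check is a comparison of provisions, followed by an illustration on assumed rates.

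**1. The two rules on the same case.** Take a serious event that is on the list, has a plausible time relation to a session, and could also be due to the stroke.
- Section 8.3.3.2 and Table 4: graded on timing and judgment. The stroke as an alternative cause is compatible with 'possible'.
- Section 8.3.3.3: generally attributed to the stroke.
- Precedence: none stated. Section 8.3.3.2 has both opinions communicated when investigator and sponsor disagree, but does not say which grade feeds the endpoint or the halt rule.

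**2. Direction.** The presumption moves events from related to unrelated and never the reverse. Applying it alike to both blinded arms does not cancel this for events caused by the field, since those arise only in the active arm. Events caused by the exercise sessions can arise in both arms.

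**3. Reach.**
- Related-SAE endpoint: affected for listed events.
- Halt rule: affected only for Grade 4 or higher events that case review would grade probable or causal. An event graded 'possible' would not trigger it in any case.
- 24-hour reporting: not affected, since section 8.3.6 requires it for all SAEs whatever the grade.
- All-event incidence and the Fisher comparison: not affected.

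**4. Illustration.** The protocol gives no event rates. Assume a background of 1% to 5% and a device-caused excess of 1 to 5 percentage points. Take 75 per arm (150 randomized 1:1) and, at the maximum sample size, 172 per arm (344 / 2).
- Expected device-caused events in the active arm = n × excess: 75 × 0.01 = 0.75 to 75 × 0.05 = 3.75.
- Chance of at least one = 1 − (1 − excess)^n: 1 − 0.99^75 = 53%; 1 − 0.95^75 = 98%.
- If the presumption were applied to every one of them, all would count as unrelated.
- Exact power of Fisher's test (two-sided 0.05) to show the excess for that one event type: 0.2% to 17% at 75 per arm, and 3% to 65% at 172 per arm.

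The comparison that ignores relatedness is therefore a weak substitute for individual grading when one event type is at issue.

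**5. A tempting figure, and its limits.** With a larger assumed excess of 5 to 8 points over a 2% to 5% background, 75 × 0.05 = 3.75 and 75 × 0.08 = 6, so about 4 to 6 device-caused events. Fisher's test gives:

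| Sham | Active | p |
|---|---|---|
| 0/75 | 6/75 | 0.028 |
| 0/75 | 4/75 | 0.12 |
| 2/75 | 8/75 | 0.098 |
| 4/75 | 10/75 | 0.16 |

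The first row needs the top of the assumed range and perfect attribution, so that no background event in either arm is rated related. The last two rows add the background (75 × 0.02 = 1.5, about 2; 75 × 0.05 = 3.75, about 4) to both arms. The first row is not an estimate of what the rule would cost.

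**The case against.** A reader might infer that the rule overrides case-level causality for any SAE above 1%, so that a device raising a common event would yield no endpoint events and no halt. The protocol does not support that reading.

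- The text says 'generally'. It is a presumption that can be rebutted, and grading by investigator and sponsor stays mandatory for every event.
- Table 4 lets a relationship be excluded when the event can be attributed to another cause, including underlying illness. Section 8.3.3.3 can be read as guidance on that criterion. The 'possible' fallback for undeterminable cases does not, by itself, cover an event with a recognized alternative cause.
- Section 10.1.2 also requires suspension on suspicion of an unacceptable risk, and under 10.1.6 the DSMB sees accumulating data and may recommend stopping. Neither needs a relatedness grade.
- Section 9.4.4 already compares event rates between arms regardless of relatedness.
- The protocol reports no device- or procedure-related events to date, so it gives no basis for any particular excess.

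All of this stands, and it rules out the stronger reading. It does not remove the inconsistency. A criterion weighed case by case is not the same as a default set by class frequency, and Table 4 also allows 'possible' alongside an alternative cause. Neither the all-event comparison nor the DSMB's review corrects the count for an endpoint defined by relatedness.

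**Conclusion.** The point holds as an unreconciled conflict with a known direction. A causality presumption sits under Expectedness, it pulls against individual grading in 8.3.3.2, and the protocol does not say which governs. Followed as written, it can only lower the related-SAE count and, within the narrow class described above, the input to the halt rule.

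The size cannot be computed from the protocol. It depends on which events are on the unseen list, how firmly raters apply 'generally', the true event rates, and which Table 4 grades count as related for the endpoint. The figures above are illustrations on assumed rates. The efficacy analysis is not touched.

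**What to change.** - In 8.3.3.3, confine the manual-of-procedures list to expectedness and background context, and remove the statement about attribution. Suggested wording: SAEs on the list are rated as expected; relatedness of every SAE is graded individually under Table 4, blinded to arm, and that grade feeds the related-SAE endpoint.
- In 9.4.4, add a table of listed SAEs by arm regardless of rated relatedness.
- Sections 8.3.3.2, 8.3.3.3 and 10.1.2 must be reconciled so that it is clear which causality determination the halt rule reads. The content of that rule is for the sponsor and the DSMB.

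The cost is a short wording change and one table, with no new data collection. The downside is that the count of related SAEs may rise in both arms.

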8.3.4 TIME PERIOD AND FREQUENCY FOR EVENT ASSESSMENT AND FOLLOW-UP

Investigators or designee will record all qualifying events (adverse events and device deficiencies) with start dates occurring any time after informed consent is obtained until the last day of study participation. At each study Visit, the Investigator or designee will inquire about the occurrence of AE/SAEs since the last visit and or last treatment. Only SAEs unresolved at the last study visit will be followed for outcome information until resolution or until assessed as chronic or stable.

8.3.5 ADVERSE EVENT AND DEVICE DEFICIENCY REPORTING

The occurrence of an AE or SAE may come to the attention of study personnel during study Visits and interviews of a study subject presenting for medical care, or upon review by a study Monitor.

All AEs including local and systemic reactions will be captured on the appropriate CRF. Information to be collected includes event description, (and time, for serious events occurring during the study procedure) onset, Investigator's assessment of severity, seriousness, relationship

³⁸ Per the recommendation in the US FDA "Guidance for Clinical Investigators, Sponsors, and IRBs Adverse Event Reporting to IRBs - Improving Human Subject Protection" (§§ III.B and IV), and in agreement with §§ 812.46(b), 812.150(b)(1), and § 8.2.5 of ISO 14155:2011/COR1:2011 and § 9.2.5 of ISO 14155:2020.

to study device/procedure (assessed only by those with the training and authority to make a diagnosis), expectedness, date (and time, for serious events occurring during the study procedure) of resolution/stabilization of the event, where applicable; and any action taken. All AEs occurring while on study must be documented appropriately regardless of relationship. During the study, all AEs will be followed to adequate resolution or stabilization. In case of adverse events that are still unresolved at the final study Visit; refer to § 8.3.4 for guidance on event follow-up.

Any medical condition that is present at the time that the participant is screened will be considered as baseline and not reported as an AE (refer to § 8.3.1). However, if the study subject's condition deteriorates at any time during the study, it will be recorded as an AE. The AE term in the latter case must be the same term entered at baseline for the preexisting condition and must start with "Worsening of.../ Deterioration of...".

Changes in the severity of an AE will be documented to allow an assessment of the duration of the event at each level of severity to be performed. If an ongoing AE worsens in its severity or its relationship to the study device or procedure changes, a new AE entry for the event should be entered on the CRF while the preceding event record should be reported as ended on the same date (113). AEs characterized as intermittent require documentation of onset and duration of each episode.

Laboratory safety measurements and variables reporting

The treating site will perform laboratory analyses according to the protocol-defined Visit schedules and determine protocol-defined parameters. A tabulation of the normal ranges for each parameter required will be enclosed with the measurements done. If at any time a subject has laboratory parameters obtained from a different laboratory, the normal ranges for that laboratory must be recorded with the result obtained. At any time during the trial, abnormal laboratory parameters which are clinically relevant (eg, which lead to interruption of trial treatment, or which lead to clinical symptoms or signs requiring therapeutic intervention), whether specifically requested in the protocol or not, must be recorded on the appropriate CRF form. When abnormal laboratory parameters or test results constitute an SAE, a complete SAE report on the SAE Report form must also be provided.

Notification of deaths

All deaths must be reported to the Sponsor, irrespective of whether the death is related to the device and/or procedure or is an unrelated event. If multiple adverse events are considered to be "causes of death", each event must be entered as a separate AE record. Whenever a subject dies and there is no known cause of death, with no AEs to which the death can be attributed (death

	The efficacy of a frequency-tuned electromagnetic field treatment in facilitating the recovery of subacute ischemic stroke patients – a pivotal study		
	No. BQ5	Ver. 4	Page 74 of 150

certificate indicates no known cause of death), the AE Term must be entered as “Unknown cause of death”.

Device deficiencies

Device deficiencies will be reported on the appropriate CRF form.

Device deficiencies that did not lead to an adverse event but could have led to a serious adverse device effect

- a. if suitable action had not been taken, or
- b. if intervention had not been made, or
- c. if circumstances had been less fortunate,

shall be reported as an SAE (please refer to § 8.3.6).

8.3.6 SERIOUS ADVERSE EVENT REPORTING

Investigator's Responsibilities

Collection, recording, and reporting of SAEs/SADEs or device deficiencies that could have led to a SADE by Investigators to the Sponsor, including any unexpected serious adverse events or serious health threats (refer to § 8.4 below), will be done in an expedited manner using the AE/SAE Report form. Any intercurrent illness, medications, and/or conditions must also be recorded using the relevant CRF form, in the normal manner. All AEs defined as serious and any device deficiencies that could have led to a SADE should be reported to the Sponsor by the Investigator within a very short period of time and under no circumstances should this exceed 24 hours following knowledge of the SAE³⁹. Receipt of SAE reports will be acknowledged by the Sponsor.

Contact details for safety reporting purposes:

[name]

Email: [contact]

³⁹ In agreement with the US FDA “Guidance for Industry and Investigators Safety Reporting Requirements for INDs and BA/BE Studies” (December 2012) and the provisions of § 7.2 of the EC Guidance on “Clinical Investigations: Serious Adverse Event Reporting under Directives 90/385/EEC and. 93/42/EEC” (MEDDEV 2.7/3 revision 3, May 2015).

Sponsor's Responsibilities

Reporting of serious adverse events by the Sponsor to regulatory authorities⁴⁰ will be done in accordance with the standard operating procedures (SOPs) of the Sponsor or designee (eg, contract research organization [CRO]) and the appropriate regulatory requirements⁴¹.

In general, reportable events⁴² will be reported at the same time to all regulatory authorities in whose jurisdiction this clinical investigation has commenced.

Data and Safety Monitoring Board (DSMB) be established in the study under the provisions of § 10.1.6. BrainQ Technologies Ltd. will also report all relevant safety information to the DSMB, according to written procedures.

8.3.7 REPORTING EVENTS TO PARTICIPANTS

Not applicable.

8.3.8 EVENTS OF SPECIAL INTEREST

Adverse events severity of which corresponds to Grade 3 or higher on the CTCAE v.5.0 scale and that have “probable”, “possible” or “causal” relationship with the device and/or the procedure, in accordance with the causality of adverse events as presented in [Table 4](#), must be reported to the Sponsor within 24 hours following the awareness by study personnel at a participating site, unless such events meet the definition of a serious adverse event provided in § 8.3.2, in which case their reporting must adhere to the provisions of § 8.3.6 of this protocol.

8.3.9 REPORTING OF PREGNANCY

Any pregnancy within the term of participation of a subject in the study must be reported by Investigator to the Sponsor. The pregnancy should then be followed-up by the Investigator to determine outcome, including spontaneous or voluntary termination, and the presence or absence of any birth defects, congenital abnormalities, or maternal and/or newborn complications.

⁴⁰ These are referred to as National Competent Authorities (NCAs) in the European Union

⁴¹ In the United States, this will be done in accordance with 21 CFR 812.812.150(b)

⁴² The part of the serious adverse event definition in § 8.3.2 appearing in italics is introduced in ISO 14155:2020 is absent from the definition available in CHAPTER I Article 2(58) of the MDR. For the purposes of this trial, the definition in this protocol will apply for Investigator reports to the Sponsor. Applicability of the gap between the definitions in this protocol and the aforementioned MDR definition will be assessed for Sponsor reports to National Competent Authorities if and where MDR will apply to this trial.

NOTE: Pregnancy follow-up does not extend the study for each subject and no data will be collected after the specified study duration for each subject.

